For each Aim 3 outcome that is collected via both medical record review and patient survey, the primary analysis will be among patients with complete outcome data from both the medical record and patient survey. Sensitivity analyses will be conducted by imputing missing outcome data using different assumptions and applying the primary analysis method to the resulting data sets. Sensitivity analyses will include (1) imputation of negative responses (i.e., responses indicating that the outcome has not occurred) for all missing patient survey responses, followed by analysis of all patients with medical record review data; (2) imputation of positive responses (i.e., responses indicating that the outcome has occurred) for all missing patient survey responses, followed by analysis of all patients with medical record review data; and (3) multiple imputation of all missing outcome data using the observed outcomes and covariates, followed by analysis of all patients selected for follow-up.

In participants who are CAPTURE+, change in CAT score will be analyzed using mixed models with a random effect for practice. The average cluster sample proportion of patients who experience exacerbations will be compared between intervention groups using methodology similar to that used for the primary endpoint. Subject to having sufficient mortality events, survival analysis allowing for correlation of endpoints within cluster (practice) will be used to compare mortality between

intervention groups and perform multivariable analysis. We will explore differences between intervention groups in the average cluster sample rate of hospitalizations again using GEE. All additional secondary analyses will also be applied to patients with clinically significant and spirometrically defined COPD, Mild COPD, PRISM, and symptomatic non-obstruction. Practices that do not have any patients with these conditions will not contribute to analyses of these secondary endpoints, respectively.

Model selection in GEE secondary analyses will be based on statistical significance at the 0.05 level using robust sandwich estimation of variability within clusters. Model fit will be checked by comparing observed versus predicted values within predefined subgroups of interest (sex, ethnic subgroups, rural and urban location, and educational status).

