| Assess the impact of CAPTURE education and patient-level CAPTURE information on clinician interventions specific to smokers who are CAPTURE+. | Proportion of CAPTURE+ participants currently smoking at the baseline study visit who have any of the components of the Aim 3 primary endpoint or any of the following occur within 12 months of baseline (evaluated as a composite endpoint and as individual endpoints): 1) clinician counseling or recommendation for smoking cessation, 2) referral to a smoking cessation program, 3) referral to a smoking quit line, and 4) newly prescribed medication for smoking cessation. |
| Determine the impact of CAPTURE education and patient-level CAPTURE information on patient symptoms, exacerbations, hospitalizations, and mortality among CAPTURE+ patients. | In CAPTURE+ participants, change in CAT score between baseline and follow-up at 12 months after baseline, and proportion of patients who experience exacerbations, hospitalizations, or mortality within 12 months of baseline. |
| Determine the impact of CAPTURE education and patient-level CAPTURE information on identification and management of patients with respiratory burden. | All of the above endpoints for Aim 3, in the population of participants defined by each of the following instead of CAPTURE+ status: 1) clinically significant COPD, 2) spirometric COPD, 3) preserved ratio, impaired spirometry (PRISM), and 4) symptomatic non-obstructed (SNO). |
| Determine the potential impact of SARS CoV-2 infection on clinical actions taken in response to CAPTURE screening. | All of the above endpoints for Aim 3, in all of the analysis populations named above, separated into cohorts based on enrollment date and the degree to which follow-up may have been affected by the SARS-CoV-2 pandemic. |

6 Study Methods for Cluster Randomized Trial (CAPTURE Protocol Aim 3)

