| New prescription for respiratory medication (long acting bronchodilator, inhaled steroids, oral anti-inflammatory) | Formal smoking cessation program referral/completion |
| Exacerbation like event assessment (hospital, ED, minute clinic, antibiotic/steroid prescription/administration) | Referral to a smoking quit line |
| Vaccination status | |
| Formal pulmonary rehabilitation program referral/completion | |

Statistical Analysis Plan

CAPTURE

| | |
|--|--|
| Data related to COVID-19 confirmed and suspected cases | |
|--|--|

Table 4: Data from clinical visits to be collected at follow-up by telephone, secure web-based server, or mail- based methodologies directly from participants and administered by COPD Foundation study personnel includes:

| All participants undergoing 12-month follow-up as described in section 6.1 | Current Smokers Only |
|--|--|
| Spirometry referral/completion | Referral to a smoking cessation program |
| New diagnosis of COPD | Referral to a smoking quit line |
| Referral to pulmonologist or other respiratory specialist | New prescription for smoking cessation medication |
| Exacerbation like event assessment | Over-the-counter patches/gum for smoking cessation |
| New prescription for respiratory medication (long acting bronchodilator, inhaled steroids, oral anti-inflammatory) | |
| CAT score | |
| Attendance of pulmonary rehabilitation | |
| COVID-19 related questions | |

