Change in CAT score and change in number of episodes of respiratory illness requiring antibiotic/steroid treatment will be analyzed using mixed⁵ models with a random effect for practice. The average cluster sample proportion of patients who experience exacerbations will be compared between intervention groups using methodology similar to that used for the primary endpoint. Subject to having sufficient mortality events, survival analysis⁶ allowing for correlation of endpoints within cluster (practice) will be used to compare mortality between intervention groups and perform multivariable analysis. We will explore differences between intervention groups in the average cluster sample rate of hospitalizations again using GEE.

Secondary Analyses Using Single Imputation: Primary and secondary efficacy analyses of outcomes collected via both medical record review and patient survey will be repeated among patients with complete medical record review data, imputing a single value for missing outcome components from the patient survey. One analysis will impute a negative outcome (i.e., the event did not occur) for each missing survey response; another analysis will impute a positive outcome (i.e., the event did occur) for each missing survey response. Complete-data analyses described in sections 11.1 and 11.2 will be performed on each complete data set produced by imputation.

Secondary Analyses Using Multiple Imputation: Primary and secondary efficacy analyses will be repeated using data sets generated by the multiple imputation procedure described in section 9.5. Complete-data analyses described in sections 11.1 and 11.2 will be performed on each complete data set produced by multiple imputation. Parameter estimates and standard errors will be

combined across the multiply imputed data sets using the method of Rubin⁸, which is implemented by the `pool()` function in the R package ‘mice’. Specifically, for each parameter of interest, let Q_i be the parameter estimate from data set i , with associated complete-data variance U_i . Let m be the number of imputed data sets. Then

$$\bar{Q} = \frac{1}{m} \sum_{i=1}^m Q_i \text{ (the average of the } m \text{ estimates)}$$

is the overall parameter estimate. Let

$$\bar{U} = \frac{1}{m} \sum_{i=1}^m U_i \text{ (the average of the } m \text{ variances)}$$

and

$$B = \frac{1}{m-1} \sum_{i=1}^m (Q_i - \bar{Q})^2 \text{ (the variance in estimates between data sets).}$$

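### The listed exacerbation test ignores repeat events, and the only planned count analysis is an unlisted change score; a baseline-adjusted rate model would use the counts better

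*SAP*

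**What the plan says.** SAP section 5.1, Table 1, lists the endpoint in CAPTURE+ participants as the "proportion of patients who experience exacerbations, hospitalizations, or mortality within 12 months of baseline". Protocol sections 1.1 and 3 list the same endpoint.

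The planned test is in SAP 11.2: "The average cluster sample proportion of patients who experience exacerbations will be compared between intervention groups using methodology similar to that used for the primary" composite. Protocol 9.3.2 says the same ("The average cluster sample proportion of patients who experience exacerbations will be compared between" intervention groups). The primary method, set out in SAP 11.1, is an identity-link GEE on a binary outcome with practice as cluster.

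SAP 11.2 holds two related plans:
- In the sentence before the exacerbation test: "change in number of episodes of respiratory illness requiring antibiotic/steroid treatment will be analyzed using mixed" models with a random effect for practice. This analysis is not among the endpoints in Table 1 and is not in Protocol 9.3.2.
- For hospitalizations, a comparison of the "average cluster sample rate of hospitalizations again using GEE".

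On data, SAP Table 3 (section 7.6) lists "Exacerbation like event assessment (hospital, ED, minute clinic, antibiotic/steroid prescription/administration") from the medical record, and Table 4 lists an exacerbation assessment from the patient survey. Neither table says whether a count or a yes/no is recorded.

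**The concern.** Exacerbations recur. Under any-versus-none, a patient who goes from three events to one contributes nothing to the treatment difference. Fewer exacerbations is part of the long-term goal stated in Protocol 2.1, so a lower event burden is what this secondary outcome ought to be able to show.

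The planned episode-count analysis shows that the SAP expects a count of treated episodes at baseline and at follow-up. But it uses that count as a change score in a linear mixed model, without listing it as an endpoint or saying how it relates to the proportion. A change score carries the variance of the baseline count as well as the follow-up count, and treated-episode counts are likely to be skewed with many zeros. At stake is some efficiency, and clarity about which exacerbation result is to be read as the main one.

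**Working it through.** **The plan's own power table.** No power is stated for exacerbations. As a check on the method, the SAP 8.2 table for the primary composite was rebuilt: 5% control rate, 44 clusters per arm, 5 patients per cluster, two-sided 5%. Effective n per arm = 220/(1 + 4 x ICC), with an unpooled z test.

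| ICC | Effective n | Rebuilt, +7.5/+10/+15 points | Stated |
|---|---|---|---|
| 0.05 | 183.3 | 0.727 / 0.899 / 0.994 | 0.72 / 0.89 / 0.99 |
| 0.10 | 157.1 | 0.660 / 0.850 / 0.985 | 0.65 / 0.84 / 0.98 |
| 0.15 | 137.5 | 0.603 / 0.800 / 0.971 | 0.59 / 0.79 / 0.97 |

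All cells agree within 0.02.

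**Inputs for the illustration.** From SAP 13.1: 67 practices with 10 CAPTURE+ patients each, so 67 x 10 / 2 = 335 per arm. ICC 0.05 is the lowest of the SAP's three values. n_eff = 335/(1 + 9 x 0.05) = 231. This omits the SAP's allowance for unequal cluster sizes. Assumed, not in the documents: negative-binomial counts, control mean mu0 of 0.2-1.0 events/year, dispersion k of 0.5-2, rate ratio 0.70 or 0.85, equal follow-up, and the same ICC for the count as for the binary outcome.

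**Formulas.**
- P(any) = 1 - (1 + k mu)^(-1/k)
- Binary: z = (p0 - p1)/sqrt((p0 q0 + p1 q1)/n_eff)
- Count, unadjusted: z = ln(1/RR)/sqrt((1/mu0 + 1/mu1 + 2k)/n_eff)

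**Example: mu0 = 0.6, k = 1, RR = 0.70.**
- Binary: p0 = 1 - 1/1.6 = 0.375 and p1 = 1 - 1/1.42 = 0.296, so z = 1.81 and power is 44%.
- Count: ln(1/0.70) = 0.357 and the variance is (1/0.6 + 1/0.42 + 2)/231 = 0.0262, so z = 2.20 and power is 60%.

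**Results.** Power at k = 1 as binary vs count, with the gain in points over k = 0.5-2:

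| Events/yr | RR 0.70 | Gain | RR 0.85 | Gain |
|---|---|---|---|---|
| 0.2 | 26.9% vs 30.2% | 2.7-4.1 | 9.7% vs 10.6% | 0.8-1.0 |
| 0.4 | 38.3% vs 47.9% | 8.4-10.5 | 12.1% vs 14.8% | 2.6-2.7 |
| 0.6 | 44.0% vs 59.7% | 13.9-16.1 | 13.3% vs 18.0% | 4.1-5.0 |
| 1.0 | 48.1% vs 73.1% | 21.8-25.0 | 14.1% vs 22.7% | 6.4-10.4 |

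At RR 0.70 and 0.4-1.0 events/year, the gain is about 7-23 points at ICC 0.10 and 6-21 at ICC 0.15. If only 65% are analysed (survey completion in SAP Table 9), n_eff = 335 x 0.65/(1 + 5.5 x 0.05) = 171 and the gain is 7-22 points.

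**The planned change score.** Take v = mu + k mu^2, a baseline mean equal to mu0 in both arms, and baseline-to-follow-up correlation rho. Then z = (mu0 - mu1)/sqrt(V/n_eff), where V sums v_follow + v_base - 2 rho sqrt(v_follow v_base) over the two arms. Power at k = 1, RR 0.70:

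| Events/yr | rho 0.2 | rho 0.4 | rho 0.6 | Unadjusted count |
|---|---|---|---|---|
| 0.4 | 29.7% | 37.6% | 51.7% | 47.9% |
| 0.6 | 37.4% | 47.1% | 63.3% | 59.7% |
| 1.0 | 47.5% | 58.9% | 75.8% | 73.1% |

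The change score is behind the unadjusted count at rho 0.2-0.4 and ahead at 0.6. Adjusting for the baseline count removes this trade-off. With equal variances and a linear model, the change-score variance is proportional to 2(1 - rho) and the adjusted variance to 1 - rho^2. The ratio of adjusted to change score is (1 + rho)/2: 0.60 at rho 0.2, 0.70 at 0.4, 0.80 at 0.6. It is below 1 for every rho below 1.

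**The case against.** A reader might infer that the plan throws the counts away and analyses exacerbations only as a binary outcome. The documents do not support that: the sentence before the exacerbation test analyses the number of treated episodes, and a patient going from three treated episodes to one does count there. What remains is a choice between count models, plus an unlisted analysis.

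A reader might also infer that a 12-month count of all exacerbation-like events is ready to use. The follow-up tables do not show this; only a treated-episode count can be inferred, from SAP 11.2.

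Other points stand:
- The hospitalization analysis is weak precedent. Table 1 lists that outcome as a proportion, and the rate wording in SAP 11.2 gives no link, offset or count definition.
- A yes/no can be combined across chart and survey as recorded in either. A count needs a combining rule.
- The positive and negative single imputations in SAP 9.5 are defined for binary outcomes and do not carry over to a count.
- Protocol 9.1.2.2 calls the secondary practice-behavior analyses exploratory, without a power calculation, and SAP 9.7 says their p-values will be read with caution.
- The intervention is education plus score-sharing, so a rate ratio nearer 1 is plausible. At 0.85 both tests are weak and the choice matters little at low event rates.

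One defence is only partial. The mixed model might include the baseline count as a covariate, which would remove most of the change-score inefficiency. The SAP does not say so, and a linear model for a skewed count would remain.

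**Conclusion.** The point holds in a limited form. The listed exacerbation endpoint is tested only as any-versus-none, and that test ignores repeat events. The one count analysis is unlisted, covers treated episodes only, and takes a form that is less efficient than the follow-up count adjusted for baseline.

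The gain cannot be fixed from the documents. Under the assumptions above it runs from about 1 point (rate ratio 0.85, 0.2 events/year) to about 25 points (rate ratio 0.70, 1.0 events/year), for an unadjusted count against any-versus-none. The count test was ahead in every scenario computed; against the planned change score, that is assured only once baseline is adjusted for. No stated power target is breached, and the binary test matches the endpoint as listed. This is a cheap improvement, not an error that threatens the trial's conclusions.

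**What to change.** Before unblinding, in SAP 11.2:

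1. Replace the change-score model with a log-link Poisson GEE on the 12-month count of treated episodes. Use practice as cluster, exchangeable correlation and robust variance. Adjust for the baseline 12-month count and add an offset for observed time where it varies. Report the rate ratio with its 95% CI.
2. Keep the any-versus-none proportion as the listed endpoint, with its existing binary imputation analyses.
3. List the count analysis in SAP Table 1 and Protocol 9.3.2, and say how it relates to the proportion.
4. Name one source for the count, or a rule for combining chart and survey.
5. Extend the count to all exacerbation-like events only if the forms record it.

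The cost is one model in place of another, on data that SAP 11.2 already presupposes, plus the work of writing the source rule. The downside is that frequent exacerbators carry more weight in a rate; the robust variance and the retained proportion limit that.

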Patients who are eligible and agree to participate in the study sign informed consent, complete the CAPTURE questionnaire, PEF testing, spirometry testing, other respiratory questionnaires, provide past medical history, and demographic information. Local/PBRN study coordinators perform the study procedures and record baseline information into the electronic data capture (EDC) system. The study coordinators calculate a CAPTURE score for each participant. For patients in a practice randomized to CAPTURE+COPD education, their practitioner is provided with CAPTURE results for their patient. Practitioners at sites randomized to the COPD education only intervention are blinded to CAPTURE scores. Practitioners in both intervention arms are blinded to research spirometry results.

Based on the data collected at baseline, participants will be classified into the following groups for analyses:

| Cohort | Definition |
|------------------------------|---|
| CAPTURE+ | Participants with 
 • CAPTURE score ≥ 5, or • CAPTURE score of 2, 3, or 4 with a low PEF, defined as <350 L/min for males and <250 L/min for females |
| CAPTURE- | Participants with 
 • CAPTURE score < 2 or scores 2-4 with normal PEF (defined as ≥ 350 L/min for males and ≥ 250 L/min for females) |
| Spirometrically Defined COPD | Participants with abnormal spirometry, defined as post-bronchodilator $FEV_1/FVC <0.7$. If a participant is unable to complete a post-bronchodilator spirometry |

| | |
|--|---|
| | (refusal, technical error on the part of coordinator, etc.), and the pre-bronchodilator FEV_1/FVC is less than 0.65, the participant will be considered to have COPD for the purpose of follow-up in this study. |
| Clinically Significant COPD | Participants with abnormal spirometry, defined as spirometrically defined COPD plus at least one of the following: 
 • $FEV_1 < 60\%$ predicted or • ≥ 1 exacerbation like event within the past 12 months. |
| Mild COPD | Participants with spirometrically defined COPD plus both of the following: 
 • $FEV_1 \geq 60\%$ and • No prior history of ECOPD |

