Height and Weight: Height and weight will be recorded in order to determine appropriate prediction equations for spirometry and possible effect of obesity on spirometry. Height will be recorded in inches, and weight will be measured in pounds.

Demographic Data Collection: Demographic data including date of birth, gender, ethnicity, race, educational level, current employment status, living arrangement and health insurance will be entered into the EDC system.

Medical History: Previous medical diagnoses will include comorbidities such as cardiovascular, respiratory, and malignant disorders. Influenza vaccination history will also be recorded.

Statistical Analysis Plan

CAPTURE

Concomitant Medication Review: Respiratory medications will be recorded at baseline for all participants.

CAPTURE Additional Items Questionnaire: Participants will complete the 13 item self-administered questionnaire.

COPD Assessment Test (CAT): Participants will complete the eight item self-administered questionnaire. Each item is on a scale of 0-5 with higher scores indicating worse health status.

Respiratory Symptoms, Smoke Exposure and Exacerbation-Like Events: History of respiratory symptoms and exacerbation like events over the past year as well as smoke exposure (including e-cigarette or equivalent) will be recorded.

Adverse Events: Adverse events related to study procedures will be recorded by the coordinator.

Practice Characteristics: The locations of participating clinical practices will be categorized based on designation as rural by the Federal Office of Rural Health Policy (FORHP) / Health Resources & Services Administration (HRSA). A practice location will be classified as rural if the ZIP code appears in the Eligible ZIP Codes file downloadable from the FORHP website: <https://www.hrsa.gov/rural-health/about-us/definition/datafiles.html>. Other data describing the characteristics of participating practices will be collected from study site personnel.

6.6.2: Longitudinal follow-up

Follow-up efficacy assessments are collected from the time of baseline to 12 months in selected cohorts (as described in section 6.1).

Table 3: Data collected from medical records include:

| All participants undergoing 12-month follow-up as described in section 6.1 | Current Smokers Only |
|--|--|
| Clinical spirometry ordered or administered | Smoking cessation counseling |
| New recorded clinical diagnosis of COPD | New prescription for smoking cessation medication |

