9.4 Covariates and Subgroups

The effect of the CAPTURE intervention will be explored in predefined subgroups of interest with results tabulated (estimated difference in average proportion of CAPTURE+ patients per practice meeting composite endpoint between intervention arms by subgroup, corresponding 95% confidence interval and p-value) as well as displayed via forest plots. These analyses will proceed similarly to that described for the primary endpoint in section 11.1. Individual-level covariates used to define subgroups of interest are categorical age (45-59 years, 60-69 years, 70-80 years), gender (Male, Female), race (American Indian/Alaska Native, Asian, Native Hawaiian or Other Pacific Islander, Black or African American, White, Unknown or Not Reported), ethnicity (Hispanic/Latino, Non-Hispanic/Latino, Unknown or Not Reported), educational status (Less than High School Graduate, High School Graduate/GED, Vocational/Some College, College Degree, Professional/Graduate Degree, or Not Reported), insurance status (private, public, none), living arrangements (alone, not alone), employment status (working, not working, unknown), smoking status (Current, Former, Never), asthma history, baseline respiratory medications (short-acting bronchodilator, maintenance respiratory medication, or none), cardiac morbidity, COPD Assessment Test (CAT) score (10 or above versus less than 10), BMI (Below 25.0 [Normal/Underweight], 25.0-29.9 [Overweight], 30.0-39.9 [Obese], 40.0 and Above [Severely Obese]), as well as cohorts defined in section 6.1 (Spirometrically Defined COPD, Clinically Significant COPD, Mild COPD, No COPD by Spirometry, PRISm, and SNO). Practice level covariates include practice type (Part of large health system/ACO/similar, Part of academic medical center/health system, Federally Qualified Health Care Center, Independent practice, Other), location (Rural, Non-rural), being a residency site, having in-house spirometry, and number of MD/DO/NP/PA primary care clinicians (0-4, 5-9, 10 or More). Because of the possible impact of the SARS-CoV-2 pandemic on study outcomes, these analyses will be repeated in subgroups defined by whether the one-year follow-up period had entirely elapsed by March 19, 2020 (date when PBRNs paused study enrollment due to SARS-CoV-2); that is, the analyses will be repeated separately in the cohort with baseline visit completed on or before March 19, 2019, and separately in the cohort with baseline visit completed after March 19, 2019. Chart review and patient follow-up survey need not be completed by March 19, 2020 for a patient to be categorized as having pre-pandemic follow-up for this subgroup analysis.

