Then using the **geeglm** function from the **geepack** package, the R code to run the primary analysis is

```
geeglm(MetComp ~ CAPTURE,
       family = binomial(link = "identity"),
       data = final,
       id = Practice,
       corstr = "exchangeable")
```

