11.2 Secondary Efficacy Analyses

Secondary Analyses of Primary Outcome: The primary analysis as described in section 11.1 will be repeated in analysis populations 2-8 as given in section 9.3 overall and by subgroups described in section 9.4. For analysis population 1, the primary analysis as described in section 11.1 will be repeated in subgroups described in section 9.4.

In addition, multivariable GEE regression analyses will be conducted separately in populations 1-8 from section 9.3, where the primary composite outcome is modelled using individual and practice level predictors in addition to the CAPTURE intervention group. Interactions will be assessed.

Efficacy Analyses of Secondary Outcomes: All analyses in this section will be conducted (separately) for each study population 1 through 8 described in section 9.3 overall and by subgroups described in section 9.4.

We will use the GEE framework to study and describe each of the individual components of the composite outcome as they relate to the CAPTURE intervention group.

In the subset of patients who report being current smokers at baseline, we will study additional binary outcomes, such as incidence of physician counselling/recommendation to stop smoking, physician referral to a formal smoking cessation program, newly prescribed smoking cessation medication, and referral to a smoking quit line, individually and in a composite outcome that also incorporates the primary outcome components.

Multivariable GEE models will incorporate individual and practice level covariates into the analysis of individual components of the composite outcome. Model selection in multivariable secondary analyses will be based on statistical significance at the 0.05 level using GEE robust sandwich estimation of variability within clusters. Model fit will be checked by comparing observed versus predicted values within predefined subgroups of interest as given in section 9.4.

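### Past-year exacerbation history is recorded at baseline but not named as a covariate for the 12-month exacerbation and hospitalisation comparisons, nor listed on its own in the SAP's covariate and baseline lists

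*SAP*

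**What the plan says.** **Baseline collection.** SAP 7.6 records "History of respiratory symptoms and exacerbation like events over the past year as well as smoke exposure" at the baseline visit, and Protocol 8.1 says the same. SAP 9.5 expects baseline data other than spirometry to have little or nothing missing.

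**Exacerbation endpoint.** Under SAP 11.2 the "proportion of patients who experience exacerbations will be compared between intervention groups using methodology similar to that used for the primary endpoint". The code for that method in SAP 11.1 begins "geeglm(MetComp ~ CAPTURE", so arm is its only term.

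**Hospitalisation endpoint.** SAP 11.2 says: "We will explore differences between intervention groups in the average cluster sample rate of hospitalizations again using GEE". No covariate is named.

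**Multivariable models.** SAP 11.2 plans these for the composite and for mortality, and for the components it says: "Multivariable GEE models will incorporate individual and practice level covariates into the analysis of individual components of the composite outcome". It plans none for exacerbations or hospitalisations.

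**Covariate and baseline lists.** SAP 9.4 runs from age through items such as "cardiac morbidity, COPD Assessment Test (CAT) score (10 or above versus less than 10), BMI" to the COPD cohorts and practice features. SAP 10.3 is similar. Neither lists past-year exacerbation history as its own item.

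**Where history does appear.** It is one of two alternative criteria for clinically significant COPD in SAP 6.1, "≥ 1 exacerbation like event within the past 12 months", which applies only to patients with obstruction. SAP 11.2 also plans that "change in number of episodes of respiratory illness requiring antibiotic/steroid treatment will be analyzed using mixed" models with a random effect for practice.

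**The concern.** Past exacerbations are a natural baseline predictor of later ones, and the trial itself uses them to define clinically significant disease. Leaving such a variable out of the comparison of 12-month exacerbations has two costs. The estimate is less precise than the collected data allow. And if the arms differ in history, that difference carries into the estimated effect.

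Imbalance is a practical question in this design. Practices are randomised at site activation, stratified by PBRN only (SAP 7.3). Patients are enrolled afterwards, and site staff's own scoring decides who counts as CAPTURE+ (SAP 7.6). About 100 clusters are randomised. Because history is not a row of the baseline table, a reader could not see directly whether the arms were alike.

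**Working it through.** **1. The plan's own figure.** The only power figures are for the composite care endpoint and the same endpoint in COPD patients; there is none for exacerbations or hospitalisations. SAP 8.2 uses 44 clusters per arm, 5 CAPTURE+ patients each, a 5% control rate and two-sided alpha of 0.05. At ICC 0.05 the effective n per arm is 44 × 5 / (1 + 4 × 0.05) = 183.3, and power for +7.5 points is 0.721 (stated 0.72). At ICC 0.10 and 0.15 it is 0.654 and 0.596 (stated 0.65 and 0.59). The figures reproduce. They fix the cluster layout used below but do not test this point.

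**2. Do the cohorts stand in for history?** The 2020 memo in SAP 13.1 works with 10 CAPTURE+ patients per practice and roughly 2 with spirometric COPD. Even if every COPD patient were CAPTURE+, at least 8 of 10 would have no history information in the cohort variable. For the remainder, history is mixed with FEV1 below 60% predicted.

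**3. Precision for exacerbations.** The documents give no prevalence of history, event risk or risk ratio. Assumed: prevalence q of 10% to 40%, overall 12-month proportion p of 20% to 30%, risk ratio RR of 2 to 4.

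- Risk without history: p0 = p / (1 − q + q·RR). Risk difference by history: d = p0 (RR − 1).
- Share of outcome variance explained: R² = d² q(1 − q) / [p(1 − p)]. SE multiplier: √(1 − R²), an approximation that applies the same R² within and between practices.

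| q | p | RR | R² | SE multiplier |
|---|---|---|---|---|
| 0.1 | 0.2 | 2 | 0.019 | 0.991 |
| 0.2 | 0.3 | 2 | 0.048 | 0.976 |
| 0.2 | 0.3 | 3 | 0.140 | 0.927 |
| 0.2 | 0.3 | 4 | 0.241 | 0.871 |

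The third row, for example: p0 = 0.3 / 1.4 = 0.214, d = 0.429, R² = 0.184 × 0.16 / 0.21 = 0.140. Across the grid the SE falls by about 1% to 13%. At RR 1.5 it falls by less than 1%.

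**4. What that means in power.** Assume 30% versus 20%, 44 clusters per arm, 5 patients each and ICC 0.05. SE = √[(0.21 + 0.16) × 1.2 / 220] = 0.0449, which gives power 0.605. With R² of 0.03 to 0.20, power becomes 0.62 to 0.70. With 10 per practice it moves from 0.817 to between 0.83 and 0.89.

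**5. Exposure to imbalance.** The SD of the arm difference in history is √[2q(1 − q)(1 + (m − 1)·ICC) / (44m)], for m patients per practice. With q of 20% to 30%, m of 5 or 10 and an assumed history ICC of 0.02 to 0.05, it is 2.9 to 4.8 percentage points. The shift in the unadjusted risk difference is the imbalance times d. With p = 25% and RR 2 to 3, a 1.96-SD imbalance shifts it by:

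- lowest: 1.96 × 0.029 × 0.208 = 1.2 points (q = 0.2, m = 10, ICC 0.02, RR 2);
- highest: 1.96 × 0.048 × 0.3125 = 2.9 points (q = 0.3, m = 5, ICC 0.05, RR 3).

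A wider assumption, with risks of 55% with and 15% without history and an imbalance SD of 4.4 points, gives 2 × 0.044 × 0.40 = 3.5 points.

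**6. Hospitalisation.** No calculation was made. The event is likely to be rarer, and the documents give no rate.

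**The case against.** **The plan already uses history.** The change-in-episodes model draws on the baseline count, and SAP 11.2 repeats its analyses by cohorts partly defined by history. Both are true, so a reader who infers that the plan ignores exacerbation history would be wrong. But the first is a different endpoint, and the second reaches only obstructed patients.

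**The lists are not closed.** SAP 9.4 names covariates that define subgroups; it does not say that no other variable may enter a model. To infer that no planned model could contain history goes beyond the text. What the text supports is that history is not named.

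**Randomisation already deals with imbalance.** Chance imbalance is part of the clustered standard error, and a 2-SD imbalance is roughly a 1-in-20 event. It is therefore wrong to infer that the unadjusted comparison is biased or invalid. For scale, 600 patients in 100 practices with ICC 0.05 and an assumed 25% risk give SE √(2 × 0.1875 × 1.25 / 300) = 0.0395, a 95% half-width of about 7.7 points; the shifts above are less than half of that. If recruitment after randomisation caused systematic selection, one covariate would not cure it. This part of the objection stands.

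**The endpoints are secondary.** Protocol 9.1.2.2 calls the secondary practice-behaviour analyses exploratory and gives them no power calculation. This lowers the priority but does not close the gap.

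**Adjustment has a cost.** The specified model is binomial with an identity link. A further term can produce fitted probabilities outside 0 to 1 or failure to converge, especially in small subgroups or with rare events. That is a fair point, and the fix has to provide for it.

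**Conclusion.** The point holds in a limited form. Past-year exacerbation history is collected, is not named in the two GEE comparisons, and has no line of its own in SAP 9.4 or 10.3. The unadjusted analyses are valid but less precise than they could be, and an imbalance in history would not be directly visible.

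The size is modest and rests wholly on assumed inputs: an SE reduction of roughly 1% to 13% for exacerbations, and a shift of about 1 to 3.5 points at an imbalance of about two SDs. Nothing has been shown for hospitalisation. No power or precision figure in either document changes.

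Two further inferences lack support. Neither document says that history is collected as none versus any; SAP 11.2 speaks of a number of episodes. Nor can it be called complete, since SAP 9.5 only expects little missing.

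**What to change.** - **SAP 11.2:** name baseline past-year exacerbation history, any versus none and derived from the recorded history, as a fixed covariate in the GEE for 12-month exacerbations, and likewise for hospitalisations. It should not be subject to selection at the 0.05 level. Keep practice clustering and robust variance, and report the unadjusted result alongside. With the identity link, the arm coefficient is still a risk difference.
- **Fallback:** state in advance what is done if the binomial identity-link model fails, for example a Gaussian working variance with identity link and robust standard errors.
- **SAP 10.3 and 9.4:** add the variable to the baseline table and to the covariate list.
- **Hospitalisation endpoint:** while editing, align its description, which is a rate in SAP 11.2 and a proportion in SAP Table 1. The covariate applies either way.

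The cost is SAP wording, slight extra analysis work, and a small convergence risk in small subgroups or with rare events. No new data are needed.
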